1 INTRODUCTION

This statistical analysis plan is for AstraZeneca "Change Asthma Clinical Practice through Guideline Education and Implementation For All Patients with Asthma: an Evaluation of an Asthma Quality Improvement Program (short title: CARE FOR ALL: an Evaluation of an asthma QIP)" (Study code: D589BC00027) and will give a detailed description of it. This version of SAP is for final analysis plan.

This is a real-world, multi-centre prospective study to bridge the gap that exists between GINA guideline recommendations and current clinical practice by demonstrating the benefits of an asthma quality improvement program (QIP), i.e. a standardized pulmonologist-targeted GINA guideline education and practice implementation. This is an evaluation on an asthma Quality Improvement Program (QIP, including GINA guideline education/training and implementation) to understand the change of physician behaviours, which leads to the change of patient outcomes.

This statistical analysis plan is based on the 3.0 version of the research protocol on February 22, 2023, the 5.0 version of the Case Report Form on September 26, 2023.

1.1 Study Objectives

Objectives	Endpoints
Primary	

 To evaluate the change in GINA guideline-recommended treatments after guideline education and implementation. 	
 Change from baseline in the proportion of participants with an ICS-based maintenance and/or reliever treatment at week 48
Secondary	

 To describe the asthma control after guideline education and implementation. 	
Secondary Endpoint 1 Change from baseline in the proportion of participant with well-controlled asthma (ACQ-5 \leq 0.75) at week 48
 
 Distribution of ACQ-5 average scores [proportion of subjects well-controlled (ACQ-5 \leq 0.75), partly controlled (0.75 to 1.5) and not well-controlled (ACQ-5 \geq 1.5)] at weeks 12, 24, 36 and 48

 To describe the change in GINA guideline-preferred treatments during guideline education and implementation. 	
Secondary Endpoint 2 Change from baseline in the proportion of participants on the treatment of ICS-formoterol as reliever at week 12, 24, 36 and 48

 To describe the change in asthma control during guideline education and implementation. 	
Secondary Endpoint 3 Change from baseline in ACQ-5 average score at week 12, 24, 36 and 48
 
 Change from baseline in the proportion of participants achieving an improvement in ACQ-5 MCID of 0.5 units or more at week 12, 24, 36 and 48

 To describe the change in GINA guideline-recommended treatments during guideline education and implementation. 	
Secondary Endpoint 4 Change from baseline in the proportion of participants with an ICS-based maintenance and/or reliever treatment at week 12, 24 and 36

 To describe asthma related treatment patterns during the study duration. 	
Secondary Endpoint 5 Asthma related treatment patterns
 
 Asthma treatment distribution at baseline and weeks 12, 24, 36, and 48, e.g., ICS-containing medications, ICS-LABA, ICS-formoterol, oral corticosteroids, leukotriene receptor antagonists,

•	
•	
•	

1.2 Study Design

The study will select a total of around 30 Tier 2 and Tier 3 hospitals across China and enrol approximately 1500 asthma patients ≥ 14 years old with all severities from the 30 participating hospitals. To represent the real-world situation of patients, pulmonologists and treatment practice, hospital selection will include as many as provinces or municipalities in mainland China, where the altitude is below 1,500 meters, while balancing hospital grade (e.g. 10 Tier 2 and 20 Tier 3). Patients will be recruited in hospital outpatient setting, where all potentially eligible asthma patients will be consecutively approached and invited to join the study, e.g., regardless of new patients or treated, exacerbation or regular follow-up.

The QIP (i.e., GINA 2021 guideline education/training and implementation) will be delivered to pulmonologists and specialist nurses in participating hospitals at hospital level, including pulmonologist-targeted initial comprehensive education based on GINA 2021, guideline implementation performance assessment and feedback, reinforcement learning, along with multiple online and offline approaches serving as reminders and supportive tools to ensure consistent education and to facilitate the asthma management in daily clinical practice in accordance with GINA 2021 recommendation.

Immediately after last patient has been enrolled at each site, the study intervention will be initiated, i.e., the initial comprehensive training on GINA 2021 will be offered to pulmonologists and specialist nurses in this hospital. All successfully enrolled participating patients will be followed up for up to 48 weeks and return to recruiting hospital for study

visits every 12 weeks. The total participating duration in this study for each participating patient will be approximately 60 weeks.

The study aims to bridge the gap between the recommendations from GINA 2021 and current clinical practice via an asthma QIP (including GINA guideline education/training and implementation).

Figure 1 Study Design

[figure not shown]

Table 1 Schedule of Activities (participating patients related)

Study Visit	Baseline Period	Intervention Period					Details in CSP Section or Appendix
		V0	V1	V2	V3	V4	
Study Visit							
Weeks		-12 ±7	0 ±14	12 ±7	24 ±7	36 ±7	48 ±7
Informed consent ^a	X						
Inclusion and exclusion criteria	X						Sections 5.2.1 and 5.2.2
Demographics ^b	X						
Vital Sign ^c	X						
Subject status ^d	X						
Smoking status ^e	X						
Medical history (comorbidities) and medications ^f	X						
Asthma history & related treatment ^g	X						
Severe asthma exacerbation		X	X	X	X	X	
Hospitalization due to asthma exacerbation since last visit		X	X	X	X	X	Section 8.1.4
ACQ-5	X	X	X	X	X	X	Section 8.1.5.1
AQLQ(S)+12	X	X	X	X	X	X	Section 8.1.5.2
PFT	X					X	
MARS-A questionnaire	X		X	X		X	
Questionnaire of asthma knowledge for patient	X		X	X		X	
Inhale skill score for patient		X	X	X		X	
Patient's expectation for asthma treatment	X		X	X		X	

Study Visit	Baseline Period	Intervention Period					Details in CSP Section or Appendix
		V0	V1	V2	V3	V4	
Laboratory assessments within prior 3 months (if available in medical records) ^h		X	X	X	X	X	
PFT/BPT/PEF/FeNO within prior 3 months (if available in medical records)		X	X	X	X	X	
Medical records on asthma related assessment and treatment		X	X	X	X	X	
Questionnaire for Asthma Patients during COVID-19 ⁱ			X				Section 8.1.9
Patient evaluation on whose pulmonologists 1. assess symptom control, 2. watch the patient using their inhaler, educate their technique, 3. have a discussion about adherence, 4. develop or review the written asthma action plan, provide patient education, 5. had a PFT before dosage reduction		X	X	X	X	X	Section 6.1.2.3

PFT = Pulmonary Function Testing; BPT = Bronchial provocation test; PEF = Peak expiratory flow; FeNO = Fractional exhaled nitric oxide

- Informed consent must be conducted prior to performing any study procedures including data collection.
- Demographic includes patient age, gender, race, ethnicity and
- Vital signs include body mass index (BMI, calculation by height and weight)
- Subject Status education level, family monthly income, job, residence (urban communities or rural villages), etc
- Smoking status include current smoker or stopping smoking or restarting smoking, smoking pack-years
- Asthma related comorbidities, including allergic history, rhinitis, chronic rhinosinusitis, nasosinusitis, gastroesophageal reflux disease, obesity, obstructive sleep apnea, depression, anxiety, eczema, and atopic dermatitis according to ICD-10-CM. Medication includes drugs administered for these asthma related comorbidities within 4 weeks before enrolment
- Historical data, e.g., the first diagnosed date of asthma and total asthma exacerbation, total number of prescription of systemic glucocorticoid treatment for at least 3 days or emergence visit or hospitalization due to asthma exacerbations during previous 12 months (an emergency room visit due to asthma that required use of systemic corticosteroids or hospitalization due to asthma), home PEF availability, asthma symptoms, severity class evaluated by self-assessment, asthma control level, first asthma-diagnose hospital and Tiers level, hospital numbers for asthma clinic visit in past 12month, medical insurance category, Patient's expectation for asthma treatment , etc
- Clinical laboratory testing data include CBC with differentiation, blood gas analysis (pH, SaO₂, PaCO₂, PaO₂, and HCO₃⁻); C-reactive protein; skin allergen prick, total IgE or specific IgE

- i: If the patient got COVID-19 infection, then answer the questionnaire, the uninfected patients are not necessary to response. Every subject if has a new infected with COVID-19 should answer one time.

1.3 Number of Subjects

Approximately 1500 participants will provide 80% power at a significant level of 0.05 to detect a change from baseline in the proportion of patients with an ICS-based maintenance and/or reliever treatment at week 48 of 5%. The baseline proportion is assumed to be 40% and a within-participants correlation is assumed to be 0.25. The proportion of missing postbaseline assessment at week 48 is assumed to be 30%.

2 CHANGES TO PROTOCOL PLANNED ANALYSES

Not Applicable

3 DATA ANALYSIS CONSIDERATIONS

3.1 General Considerations

Unless otherwise stated, all statistical methods in the subsequent sections will be based on the following general methods. Statistical programming and analyses will be performed using SAS® (SAS Institute, Inc., Cary, NC, USA), version 9.3 or higher, and/or other validated statistical software as required

All categorical data will be presented in contingency tables, using absolute and relative frequencies. Percentages will be rounded to the first decimal place and, therefore, may not always add up to 100%. When applicable, 95% confidence intervals (CIs) will be presented with estimates of proportions. The percentages will not be presented for zero counts.

All continuous data will be summarized via relevant descriptive statistics, such as number of observations with available measurements, mean, standard deviation, median, first and third quartiles (Q1 and Q3) when applicable, minimum and maximum.

Missingness in the variables will also be presented.

Decimal points will be presented as follows: N will be presented without decimal, minimum/maximum in same precision as in the database, mean/median in one more decimal than minimum/maximum, and SD in one more decimal than mean/median. And the decimal places of SD should not be greater than 4.

3.1.1 General Study Level Definitions

The Electronic Data Capture (EDC) system will be used for data collection and query handling. Except for the questionnaires to be completed by participants, all data will be based on what have been generated during routine clinical practice, if available.

3.1.2 Baseline Definition

Unless otherwise stated, general baseline will be defined as the last non-missing evaluation on or prior to Visit 0. Baseline definitions of comorbidities and treatments are provided in the comorbidities, medications and prescriptions sections (refer to section 4.1.8 and 4.1.9).

3.1.3 Study Day

If the assessment date is on or after Visit 1 in intervention period, the study day will be calculated as: Assessment Date – Date of Visit 1 in intervention period + 1.

If the assessment or event date is prior to Visit 1 in intervention period, the study day will be calculated as: Assessment Date – Date of Visit 1 in intervention period.

3.1.4 Visit Window

A visit windowing strategy will be implemented for subjects as shown below.

Analysis visit	Target Day	Actual assessment day
Week 0	Day 1	Training day to D42
Week 12	Day 84	D43 to D126
Week 24	Day 168	D127 to D210
Week 36	Day 254	D211 to D294
Week 48	Day 336	D295 to D378

The visit will be missing if no assessment was reported within the specified visit window. If multiple assessments fall within one visit window, the scheduled visit takes priority, followed by the one closest to the target day. If two evaluations are equidistant from the scheduled time point, the earlier one will be used.

A visit windowing strategy will be implemented for investigator as shown below:

Analysis visit	Target Day	Actual assessment day
Baseline		<= Training day
Week 12	Day 84	Day2 to D126
Week 24	Day 168	D127 to D252

Week 48	Day 336	D253 to D378
---------	---------	--------------

The visit will be missing if no assessment was reported within the specified visit window. If multiple assessments fall within one visit window, the one closest to the target day. If two evaluations are equidistant from the scheduled time point, the earlier one will be used.

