4.1.8 Prior and Concomitant Medications

Prior and concomitant medications for asthma, and prior medications for asthma related comorbidities will be coded using the World Health Organization Drug Dictionary (WHO DD) of the version currently in effect at the time of database lock. The number and percentage of patients who took prior and concomitant medications for asthma, prior medications for asthma related comorbidities will be summarized respectively by ATC medication class 2 and WHO DD preferred term (PT) in the FAS. Prior and concomitant medications will also be presented in a listing.

Prior medications are defined as those medications with an end date prior to enrolment. Concomitant medications are defined as those medications which are taken on or after Visit 1 (Week 0). This includes medications which start prior to Week 0 but continue after Week 0. Multiple drug usage in the same classification and preferred term by a subject will be counted only once.

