4.1.9 Prescriptions

Prescribed medication for asthma will be coded using the World Health Organization Drug Dictionary (WHO DD) of the version currently in effect at the time of database lock. The number and percentage of patients who are prescribed for asthma will be summarized respectively by ATC medication class 2 and WHO DD preferred term (PT) and visit in the FAS. Prescriptions will also be presented in a listing.

If treatment is prescribed at least once within 3months before Visit 0 (week -12), the subjects will be regarded as receiving this treatment at baseline. For Visit 2 (week 12), if treatment is prescribed at least once on or after Visit 1 and on or before Visit 2, the subjects will be regarded as receiving treatment at this visit. For Visit 3 -Visit 5 (week 24, 36 and 48), if treatment is prescribed at least once after last visit and on or before this visit, the subjects will be regarded as receiving treatment at this visit.

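### The SAP starts its clock at both Visit 1 and the training day, so prescriptions close to the start of the intervention can be misclassified or left out at week 12

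*SAP*

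**What the plan says.** **Rules that start at V1**
- SAP 3.1.3 sets the study-day clock. From V1 onwards the day number is "Assessment Date – Date of Visit 1 in intervention period + 1". V1 is therefore always Day 1, and earlier dates get negative days.
- SAP 4.1.9 defines the week-12 prescription interval: "For Visit 2 (week 12), if treatment is prescribed at least once on or after Visit 1 and on or before Visit 2". SAP 4.2.1.1 and 4.2.2.2 refer to this section for the ICS and ICS-formoterol endpoints.
- SAP 4.1.8: "Concomitant medications are defined as those medications which are taken on or after Visit 1 (Week 0"). Prior medication must have ended before enrolment.

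**Rules that start at training**
- SAP 3.1.4 gives the week-0 window as "Training day to D42", with target Day 1.
- SAP 4.1.1 counts follow-up time from the training date.

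**Order of V1 and training**
- The Schedule of Activities (Protocol 1.3, SAP 1.2) allows V1 at week 0 ±14 days.
- Protocol 1.1 and 8 describe V1 to V5 as following the start of the intervention. Protocol 4.1 and SAP 1.2 make the initial training that start.

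**Assessments outside a window**
- SAP 3.1.4: "The visit will be missing if no assessment was reported within the specified visit window". The preference for scheduled visits applies only inside a window: "If multiple assessments fall within one visit window, the scheduled visit takes priority".

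**The concern.** Training marks the boundary between pre- and post-intervention prescribing, but the rule that sorts prescriptions into week 12 never mentions it. Unless V1 and training fall on the same day, the two origins separate. Either prescribing that the programme could not have influenced is counted as post-intervention, or prescribing that followed the training is dropped.

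The results at stake are the week-12 changes in ICS use and in ICS-formoterol reliever use, the week-12 treatment patterns, and the same items in the second interim analysis (SAP 5). Any week-0 summary is also affected. The prior and concomitant medication tables have a related gap, because they are cut at enrolment and at V1.

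**Working it through.** No stated power or sample-size figure is involved, so the check applies the date rules to possible V1 dates. One assumption is needed: week 0 in the Schedule of Activities is the training day.

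**Step 1. Study day of training.** The SAP 3.1.3 formula gives V1 Day 1. If V1 is *d* days before training, training falls on study day *d* + 1. If V1 is *d* days after training, training falls on study day −*d*.

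**Step 2. Apply the week-0 window (training day to D42) and the week-12 interval (V1 to V2).**

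| V1 relative to training | Training on study day | V1 inside week-0 window? | Pre-training days counted at week 12 | Post-training days counted nowhere |
|---|---|---|---|---|
| 14 days before | 15 | no | 14 | 0 |
| 7 days before | 8 | no | 7 | 0 |
| 1 day before | 2 | no | 1 | 0 |
| same day | 1 | yes | 0 | 0 |
| 1 day after | −1 | yes | 0 | 1 |
| 7 days after | −7 | yes | 0 | 7 |
| 14 days after | −14 | yes | 0 | 14 |

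With an early V1, week 0 is missing unless another assessment falls inside the window, and scheduled-visit priority cannot rescue it. One prescription in the pre-training days is enough to classify the patient as treated at week 12. With a late V1, days between training and V1 are too late for baseline (three months before V0) and too early for week 12.

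**Step 3. Share of the week-12 interval.** With V1 14 days early and V2 at 84 ±7 days after training, V1 to V2 spans 91 to 105 days, or 92 to 106 counting both ends. The pre-training share is 14/92 = 15.2% to 14/106 = 13.2%. The paragraph on medication taken at the end of SAP 4.2.1.2 adds a three-month limit that could drop a V1 record there. SAP 4.1.9 has no such limit.

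**Step 4. Later visits.** Weeks 24, 36 and 48 count prescriptions after the previous visit up to the current one. The week-48 interval runs from after V4 to V5 and does not touch V1 or training.

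**Step 5. Prior and concomitant medication.** Prior ends before enrolment; concomitant starts at V1. Medication that ends in the nominal 12 weeks between them is in neither class.

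**Step 6. Week-36 target.** 36 × 7 = 252. Midpoints between targets 84, 168, 252 and 336 are 126, 210 and 294, which are exactly the printed cut-offs. With 254, the last two would be 211 and 295. The windows are therefore right and the printed target of Day 254 is wrong. It matters only when choosing between assessments inside one window.

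**The case against.** **The protocol puts V1 after training.** Protocol 1.1 and 8 say so, the Schedule of Activities places V1 in the intervention period, and SAP 3.1.3 describes V1 that way too. No passage equates week 0 with the training day, so ±14 days need not mean before training. On that reading the week-0 window is coherent, because it opens on or before Day 1. This stands as a limit: the early-V1 problem is conditional. It does not remove the point, because a V1 after training produces the opposite gap, and the schedule and the text still need to be reconciled.

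**Little depends on it.** No visible primary or secondary endpoint uses week 0, the week-12 results are descriptive, and no stopping or decision rule is attached to the second interim. All of that stands.

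**The medication gap is disclosed.** Protocol 6.7 says that changes during the recruitment period are not captured. That largely explains the gap, but any such record that is in the database still has no class.

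**A reader might infer a large upward bias at week 12.** Suppose half of V1s precede training, with a 40% chance of ICS at such a V1 and 45% afterwards. The chance of at least one ICS prescription is 0.40 + 0.45 − [0.18 + ρ√(0.24 × 0.2475)], which is 60.9% at ρ = 0.25 and 48.7% at ρ = 0.75. Set against 45% and halved, this suggests 8.0 or 1.9 points. The comparison is not fair, because it sets two prescribing chances against one. In the same model, patients with V1 on or after training also have two chances: 0.45 + 0.45 − (0.2025 + 0.2475ρ), or 63.6% and 51.2%. Halving the differences gives about −1.3 and −1.2 points, so the sign reverses. The even spread of V1 dates and the 0.75 correlation are assumptions, and the other inputs are borrowed from the sample-size section.

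**Conclusion.** The SAP mixes two origins, and no rule says what happens when V1 and training fall on different days. If week 0 is the training day, up to 14 days of prescribing are placed on the wrong side (V1 early) or nowhere (V1 late). This reaches the descriptive week-12 ICS, ICS-formoterol reliever and treatment-pattern results and the second interim.

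Size and direction cannot be given from the documents, which report no V1 dates relative to training and no per-visit prescribing rates. The direction need not be uniform: the ICS-formoterol endpoint excludes concomitant SABA (SAP 4.2.2.2), so a pre-training SABA prescription could count against a patient.

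A reader might also infer two stronger conclusions that the documents do not support:
- **Bias in the primary endpoint.** The week-48 interval is untouched.
- **Altered membership of the full analysis set.** The set requires a post-intervention treatment assessment, but SAP 4.1.9 has rules for baseline and Visits 2 to 5 and none for V1. No route from an early V1 to changed membership is shown.

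The medication-class gap and the Day 254 slip hold without the week-0 assumption, and both are minor.

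**What to change.** 1. Reconcile the ±14-day allowance for V1 with the protocol text that places V1 after the start of the intervention, and state whether week 0 is the hospital's training day.
2. Use the hospital training date as the single origin for study day and visit windows.
3. Let the week-0 window include the scheduled V1 over its allowed ±14 days. Moving the origin alone is not enough, because a window that opens on the training day still excludes an early V1.
4. Start the week-12 prescription look-back at the training date, whatever the order of V1 and training. Starting at the later of the two would leave the gap between training and a late V1.
5. Classify medication as prior if taken before training and concomitant if taken on or after it; both may apply.
6. Set the week-36 target to Day 252.

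The cost is SAP wording and derivation code. The training date is already needed for follow-up time in SAP 4.1.1, and SAP 4.1.9 already relies on dated prescriptions.

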3.1.5 Handling of Unscheduled Visits

Listings will include scheduled and unscheduled data.

3.1.6 Handling of Protocol Deviations in Study Analysis

Criteria for protocol deviations will be established, and patients with protocol deviations will be identified and documented before the database lock.

3.1.7 Handling of Missing Data

Missing data will not be imputed unless otherwise specified elsewhere in the SAP.

Missing dates or partially missing dates will be imputed conservatively for adverse events and prior or concomitant medications/procedures.

For comorbidities, medications and prescriptions sections, incomplete (i.e., partial missing) date will be imputed.

Incomplete End Date:

If missing day and month, then December 31 will be assigned to the missing field.

If missing day only, then the last day of month will be assigned to the missing field.

If the death date is complete and the imputed end date is after the death date, then the end date will be imputed using the death date.

Incomplete Start Date/Baseline Prescribed Date

If missing day and month, then January 1 will be assigned to the missing field.

If missing day only, then the first day of month will be assigned to the missing field.

If the imputed start date is after the end date, then the start date will be imputed using the end date.

If the imputed baseline prescribed date is after the planned start date, then the baseline prescribed date will be imputed using the planned start date.

Otherwise, do not impute.

For incomplete asthma symptoms start date or asthma diagnosed date, the imputation will follow as below:

If missing day and month, then January 1 will be assigned to the missing field.

If missing day only, then the first day of month will be assigned to the missing field.

Otherwise, do not impute.

By-visit endpoints will be analyzed using observed data, unless otherwise specified. For observed data analyses, missing data will not be imputed and only the observed records will be included.

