4.2.1.2 Primary Analysis of Primary Endpoint

Proportion of patients with an ICS-based maintenance and/or reliever treatment will be described using the frequency with ICS and corresponding percentage at baseline and week 48.

The primary analysis will use mixed effect logistic regression model, taking the measurement timepoint (baseline/post-baseline) as the fixed effect, hospital, pulmonologist and patient as the random effects. Logit link function will be used, and the model parameters will be estimated by maximum likelihood approach. The compound-symmetry variance-covariance structure will be used. In case of lack of convergency, hospital and prescriber factors will be removed from the model.

Within the framework of this model, first predict for all patients the probability of ICS usage at baseline/ post-baseline and then take the average over baseline/ post-baseline patients to get an estimate of proportion, and finally take the difference between the two proportions as the risk difference estimate, the 95% confidence interval of risk difference in proportion by bootstrapping method will be estimated and presented. Besides, Odds Ratio and P value from the model will also be estimated and presented. The analysis will be performed in FAS. Reference SAS code is shown in section 7.

If medication is taken at least once within 3 months before Visit 0 (week -12), the patients will be regarded as taking this medication at baseline. For Visit 2 (week 12), if medication is taken at least once on or after Visit 1 and on or before Visit 2 (within 3 months before this visit), the subjects will be regarded as taking medications at this visit. For Visit 3 -Visit 5 (week 24, 36 and 48), if medication is taken at least once after last visit and on or before this visit (within 3 months before this visit), the subjects will be regarded as taking medication at this visit.

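### Incomplete medication end dates are set to the latest possible day and capped only at death, so some drugs stopped before enrolment lose 'prior' status and are tabulated as concomitant or in neither category

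*SAP*

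**What the plan says.** SAP 3.1.7 has two rules for incomplete end dates in the comorbidity, medication and prescription data: "If missing day and month, then December 31 will be assigned to the missing field" and "If missing day only, then the last day of month will be assigned to the missing field". One limit follows: "If the death date is complete and the imputed end date is after the death date", the death date is used instead. In the same section, an imputed start date is held at the end date and an imputed baseline prescribed date at the planned start date. The stated intent is: "Missing dates or partially missing dates will be imputed conservatively for adverse events and prior or concomitant medications/procedures". For by-visit endpoints the section says: "For observed data analyses, missing data will not be imputed and only the observed records will be included", subject to a proviso for anything specified otherwise.

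The dates are then used in SAP 4.1.8: "Prior medications are defined as those medications with an end date prior to enrolment", and "Concomitant medications are defined as those medications which are taken on or after Visit 1 (Week 0", which includes drugs that began earlier and continue past Week 0.

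SAP 4.2.1.2 ends with a by-visit rule based on drug taking. For Visits 3 to 5 a patient counts as a user "if medication is taken at least once after last visit and on or before this visit (within 3 months before this visit". Its baseline version looks back 3 months from V0. By contrast, SAP 4.2.1.1 defines the primary endpoint by the doctor's prescription and points to SAP 4.1.9, which asks only whether a treatment was prescribed at least once in the interval.

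**The concern.** An end date with a missing part still carries information: the drug had stopped by the time someone recorded that it had. The rule ignores this. It has no limit at enrolment, at the visit where the stop was recorded, or at study end, although the same section does apply logical limits to start dates and prescribed dates.

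The direct consequence is misclassification in the prior and concomitant medication tables, which SAP 5 also lists for both interim analyses. Stops close to enrolment are to be expected: footnote f of the schedule of activities limits comorbidity drugs to those given in the 4 weeks before enrolment, so their stop dates will often fall in the enrolment year or month.

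The indirect consequence concerns the 'taken' paragraph in SAP 4.2.1.2. If it feeds any by-visit summary, a late imputed end date makes a stopped drug look current. The latest possible date may be a cautious choice for listing concomitant drugs. It is not cautious for prior status or for a proportion of users by visit, and the SAP does not say what 'conservative' means there.

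**Working it through.** The plan states no figure on this point, so the check applies the date rules to the nominal calendar.

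**Inputs**
- Visits every 12 weeks (84 days), V0 at week -12 and V1 at week 0 (protocol 4.1 and schedule of activities). Days from V0: V1 84, V2 168, V3 252, V4 336, V5 420.
- Visit windows of 7 around V0 and 14 around V1, read as days. The V0 to V1 gap is then 84 - 7 - 14 = 63 to 84 + 7 + 14 = 105 days.
- A 365-day year, with V0 on day *d*. Enrolment is taken as the day of V0.
- Shares below are shares of calendar dates. They are shares of records only if enrolment is spread evenly over the year.

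**1. Year-only end date, drug stopped before enrolment in the enrolment year (SAP 4.1.8)**
- Imputed end minus enrolment = 365 - *d*, which is never negative. The drug is never prior.
- It is concomitant if 365 - *d* ≥ 84, so *d* ≤ 281, which is 8 October: 281/365 = 77% of dates.
- For the other 84/365 = 23% it is neither prior nor concomitant.
- With a 63-day gap the limit is *d* ≤ 302 (29 October, 83%). With a 105-day gap it is *d* ≤ 260 (17 September, 71%).

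**2. Month-only end date, drug stopped before enrolment in the enrolment month**
- The month end is on or after enrolment, so prior status is lost.
- The date moves by at most 30 days. Enrolment is at least one day after the stop, so the imputed end is at most 29 days after enrolment. V1 is at least 63 days after V0, so the drug cannot reach V1. It is in neither category.

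**3. By-visit use, only if the 'taken' rule of SAP 4.2.1.2 is applied**
- Year-only stop before enrolment in the enrolment year: counted at week 12 for *d* ≤ 281, as above. It is counted at week 24 if 365 - *d* > 168 (*d* ≤ 196, 54%), at week 36 if > 252 (*d* ≤ 112, 31%), and at week 48 if > 336 (*d* ≤ 28, 8%).
- The same record always counts as taken at baseline, because its imputed end is on or after V0, even if the true stop was more than 3 months earlier.
- Year-only stop in the calendar year before V0: the imputed 31 December lies in the 3-month baseline window for V0 dates up to about the end of March.
- Stop during follow-up, example: V1 on 10 January 2023 gives V3 on 27 June, V4 on 19 September and V5 on 12 December. A drug recorded at V3 as stopped in 2023, month unknown, gets 31 December 2023 and counts at V4 and V5, although V3 already documented the stop.
- Month-only stop during follow-up: a shift of at most 30 days can cross at most one visit boundary.

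**4. Primary endpoint**
- SAP 4.1.9 asks whether a prescription fell in the interval. No end date enters the rule, so the end-date imputation does not change the result.

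**The case against.** The strongest reply is that the plan's main results do not use these dates. The primary endpoint (SAP 4.2.1.1) and Secondary Endpoint 2 (SAP 4.2.2.2) are defined by prescription through SAP 4.1.9. SAP 3.1.7 says by-visit endpoints use observed data. Taking the latest possible end date is a familiar convention for concomitant drugs, and date queries may resolve many incomplete entries.

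Most of this stands. The prescription-based endpoints are unaffected. The observed-data sentence is a weaker safeguard, because it gives way to anything specified otherwise, and the same section says that incomplete medication and prescription dates will be imputed. The SAP does not say which analysis uses the 'taken' paragraph, although it sits in the section on the primary analysis. Secondary Endpoints 4 and 5 name no data source in their own sections. The reply does not touch the prior and concomitant tables.

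A reader might infer three stronger points, and the documents support none of them.
- That the week-48 proportion is inflated by a stated amount. This needs an assumed number of incomplete records, a convenient calendar and no other ICS in the interval. A patient who switches ICS product is still correctly a user.
- That the error favours the programme. Stops during follow-up add later users, but under the same rule baseline users are added too (step 3).
- That adherence is overstated. Protocol 8.1.6.7 names days-covered and possession measures but does not say that they use imputed end dates.

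**Conclusion.** The point holds for the prior and concomitant medication tables. A year-only stop before enrolment, in the enrolment year, is always misclassified: as concomitant for 77% of V0 dates (71% to 83% across the visit windows), and as neither for the rest. A month-only stop before enrolment, in the enrolment month, always falls into neither category.

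These are effects per affected record. The number of incomplete end dates is not given, so the effect on any table cannot be calculated. The month-only result assumes that the scheduled windows are kept. Protocol 4.1 starts the programme as soon as a site's last patient is enrolled, so a shorter V0 to V1 gap would weaken it.

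Any effect on by-visit summaries depends on whether the 'taken' rule is used, and its net direction is unknown. This is a correctable fault in descriptive tables and an ambiguity to close before database lock. It is not a threat to the primary result.

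**What to change.** Add to SAP 3.1.7 that an imputed end date may not be later than the earliest of:
- (a) the day before enrolment, for drugs recorded at V0 as already stopped;
- (b) the visit at which the stop was recorded, where the database holds it;
- (c) the end-of-study date;
- (d) the death date.

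Item (a) must be the day before enrolment and not V0 itself. If V0 is the enrolment day, an end date on V0 still fails the prior definition and, being before Visit 1, leaves the drug in neither table.

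Also state that imputed end dates do not enter the prescription-based endpoints, and reconcile the 'taken' paragraph in SAP 4.2.1.2 with the 'prescribed' rule in SAP 4.1.9, naming the analysis that uses each. The cap alone does not remove the baseline problem in step 3, since a date capped at the day before enrolment still lies in the 3-month window. If the 'taken' rule is kept for any summary, repeat that summary without the incomplete records.

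The cost is a few sentences in the SAP and a small change to the date derivation. Whether the database holds the stopped status and the visit at which it was recorded has to be confirmed, because the case report form is not among the documents. If it does, no new data are needed.
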